#### **17.7.8.2.2 Sampling fluid (SSF++) toxicity (Test 2)**

- a) A 5.0 mL aliquot of sampling solution will be inoculated with the challenge microorganism so that the final concentration will equal 30 – 100 CFU/ml of the challenge microorganism in the same manner as Test 1.
- b) Within one min after the addition of the challenge microorganism, the microorganisms will be enumerated by standard microbiological methods extant in the laboratory.
- c) Triplicate 0.75 mL aliquots will be removed and plated using TSA+N pour plates.
- d) After 30 minutes, the microorganisms will be enumerated a second time using the same procedures.
- e) This procedure will be repeated two times for a total of three replicates per test product per time point.

#### **17.7.8.2.3 Test microorganism viability control (Test 3)**

- a) A 5.0 mL aliquot of PBW will be inoculated with a volume of the challenge microorganism so that the resulting suspension contains 30 – 100 CFU/ml in the same manner as Test 1.
- b) Within one min the microorganisms will be enumerated by standard microbiological methods extant in the laboratory.
- c) Triplicate 0.75 mL aliquots will be removed and plated using TSA pour plates.
- d) After 30 minutes, the microorganisms will be enumerated a second time using the same procedures.
- e) This procedure will be repeated two times for a total of three replicates per test product per time point.

#### 17.7.8.2.4 Test product control (Test 4)

- a) A 5.0 mL aliquot of the investigational product or active control will be inoculated with a volume of the challenge microorganism so that the resulting suspension contains 30 – 100 CFU/ml in the same manner as Test 1.
- b) Within one minute the microorganisms will be enumerated by standard microbiological methods extant in the laboratory.
- c) Triplicate 0.75 mL aliquots will be removed and plated using TSA pour plates.
- d) After 30 minutes, the microorganisms will be enumerated a second time using the sample procedures.
- e) This procedure will be repeated two times for a total of three replicates per test product.

#### 17.7.9 Incubation

All plates for Tests 1, 2, 3, and 4 will be incubated for  $48\pm 2$  hours at  $35\pm 2$  °C.

#### 17.7.10 Interpretation of data

- a) The number of surviving challenge microorganisms for each replicate from each test will be average count of the three plates.
- b) The number of survivor values will be transformed to  $\log_{10}$ .
- c) The number of survivors ( $\log_{10}$ ) from each test (1, 2, and 4) will be compared to the test microorganism viability population (Test 3).
- d) Neutralization aspects of the SSF++ will be considered adequate if the mean  $\log_{10}$  CFU/ml of Test 1 is not more than 0.20  $\log_{10}$  less than the mean  $\log_{10}$  CFU/ml of Test 3 (Mean  $\log_{10}$  CFU/ml from Test 4 – Mean  $\log_{10}$  CFU/ml from Test 1 using corresponding time points).
- e) The SSF++ will be considered non-toxic if the mean  $\log_{10}$  CFU/ml of Test 2 is not more than 0.20  $\log_{10}$  less than the mean  $\log_{10}$  CFU/ml of Test 3 (Mean  $\log_{10}$  CFU/ml from Test 3 – Mean  $\log_{10}$  CFU/ml from Test 2 using corresponding time points).
- f) The mean  $\log_{10}$  CFU/ml from Test 4 must be at least 0.20  $\log_{10}$  less than the mean  $\log_{10}$  CFU/ml of Test 3.
- g) The amount of CFU added for each aspect must be confirmed to yield a final suspension containing 30-100 CFU/ml (validated in test 3).
- h) The absence of growth controls must be negative for growth.

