### 5.2.2 Bacterial Enumeration Methods

Following sample collection, vortex the sample for 15 seconds and 10-fold serial dilutions will be prepared using PBW. One ml aliquots of appropriate dilutions will be pour-plated in TSA+N. Samples must be plated within 30 minutes of collection.

Serial dilutions of collected baseline screening samples as follows:

- for groin sites: 1 serial dilution ( $10^{-3}$ )
- for abdomen sites: 1 serial dilution ( $10^{-1}$ )

Serial dilutions of collected treatment day (D0) samples as follows:

for groin sites:

- Baseline: 3 serial dilutions ( $10^{-3}$ ,  $10^{-4}$  and  $10^{-5}$ )
- 30 seconds: 4 serial dilutions ( $10^0$ ,  $10^{-1}$ ,  $10^{-2}$  and  $10^{-3}$ )
- 10 minutes: 4 serial dilutions ( $10^0$ ,  $10^{-1}$ ,  $10^{-2}$  and  $10^{-3}$ )
- 6 hours: 4 serial dilutions ( $10^0$ ,  $10^{-1}$ ,  $10^{-2}$  and  $10^{-3}$ )

for abdomen sites:

- Baseline: 3 serial dilutions ( $10^{-1}$ ,  $10^{-2}$  and  $10^{-3}$ )
- 30 seconds: 3 serial dilutions ( $10^0$ ,  $10^{-1}$  and  $10^{-2}$ )
- 10 minutes: 3 serial dilutions ( $10^0$ ,  $10^{-1}$  and  $10^{-2}$ )
- 6 hours: 3 serial dilutions ( $10^0$ ,  $10^{-1}$  and  $10^{-2}$ )

After  $72 \pm 4$  hours of aerobic incubation at  $30 \pm 2^\circ\text{C}$ , colonies will be manually counted and viable cells in the original sample will be calculated according to SOPs. After incubation, plates may be refrigerated up to 48 hours prior to counting.

Bacterial colonies enumerated manually within the countable range 25-250 from each dilution will be recorded on the appropriate CRFs for each subject. The average number of microorganisms recovered (CFU/cm^2) from the skin during screening and treatment day will be calculated using the formula to convert the volume of sample collected into  $\log_{10}\text{CFU}/\text{cm}^2$  of skin:

$$R = \log_{10} \left[ \frac{F \left( \frac{\sum_{i=1}^3 c_i}{n} \right) D}{A} \right]$$

Where:

$R$  = the average colony-forming unit count in  $\log_{10}$  scale per  $\text{cm}^2$  of sampling surface

$F$  = total number of ml of stripping fluid added to the sampling cylinder; in this study,  $F = 6$  ml

$\frac{\sum_{i=1}^3 c_i}{n}$  = average of the triplicate colony counts used for each sample collected

$D$  = dilution factor of the plate counts

$A$  = inside area of the cylinder in  $\text{cm}^2$ ; in this study,  $A = 3.80 \text{ cm}^2$  for the 2.2-cm diameter cylinder.

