#### **17.7.8.2.1 Neutralizer effectiveness (Test 1)**

- a) Out of the 6.0 mL aliquot of sampling solution taken from the volunteer, 5.0 mL will be transferred to a new sterile tube and inoculated with the challenge microorganism so that the final concentration will equal 30 – 100 CFU/ml of the challenge microorganism (the prepared inoculum will be diluted using PBW to achieve the desired concentration, a 0.1 mL aliquot from the 10^-4 dilution will be used).
- b) Within one min after the addition of the challenge microorganism, the microorganisms will be enumerated by standard microbiological methods extant in the laboratory.
- c) Triplicate 0.75 mL aliquots will be removed and plated using TSA+N pour plates.
- d) After 30 minutes, the microorganisms will be enumerated a second time using the same procedures.
- e) This procedure will be repeated two times for a total of three replicates per test product per time point.

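### The neutralization rule never compares used with clean sampling fluid, so residual kill above 0.20 log10 could pass if SSF++ on TSA+N recovers more than PBW on TSA

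*Combined protocol and SAP*

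**What the plan says.** Appendix 17.7.8.2 defines three tests that matter here.

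- **Test 1, neutralizer effectiveness.** The fluid is SSF++ that has been on treated skin: "Out of the 6.0 mL aliquot of sampling solution taken from the volunteer, 5.0 mL will be transferred to a new sterile tube". It is plated on TSA+N.
- **Test 2, sampling fluid toxicity.** "A 5.0 mL aliquot of sampling solution will be inoculated with the challenge microorganism". This is SSF++ that has not touched product. The agar is the same as in Test 1: "Triplicate 0.75 mL aliquots will be removed and plated using TSA+N pour plates".
- **Test 3, viability control.** "A 5.0 mL aliquot of PBW will be inoculated with a volume of the challenge microorganism". The agar carries no neutralizers: "Triplicate 0.75 mL aliquots will be removed and plated using TSA pour plates".

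Appendix 17.7.10 sets the acceptance rules. Item (c) says that survivors "from each test (1, 2, and 4) will be compared to the test microorganism viability population (Test 3". In words, item (d) finds neutralization adequate when mean Test 1 is at most 0.20 log10 below mean Test 3; its bracketed formula, however, subtracts Test 1 from Test 4. Item (e) finds SSF++ non-toxic when mean Test 2 is at most 0.20 log10 below mean Test 3. No item compares Test 1 with Test 2, and none limits how far Test 2 may exceed Test 3.

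**The concern.** The validation has to show that product residue carried into the sample no longer kills. Test 1 and Test 3 differ in three respects: residue, suspending fluid and agar. Test 1 and Test 2 differ only in that the Test 1 fluid has been on treated skin, so their difference isolates the residue effect. Test 2 is also the reference that resembles the main study, where every sample, baseline and post-treatment, is collected in SSF++ (section 5.2.1) and plated in TSA+N (section 5.2.2).

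If the SSF++ and TSA+N system recovers organisms better than PBW and TSA, that gain offsets residual kill in the Test 1 against Test 3 contrast, and (e) does not screen for it. The consequence would reach the efficacy data. Section 5.2.2 says "Samples must be plated within 30 minutes of collection", so active residue could go on killing for up to half an hour before plating. That would lower post-treatment counts and leave baseline counts untouched. The validation is the plan's safeguard against this.

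**Working it through.** **Inputs from the documents.** The limit is 0.20 log10 (17.7.10 (d) and (e)). Each test has three replicates per time point, each plated as three 0.75 mL aliquots (17.7.8.2.1 to 17.7.8.2.3). The challenge level is 30 to 100 CFU/ml (17.7.10 (g)). The limit is a chosen value without a derivation, so there is no figure of the plan's to reproduce.

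**Assumptions.** Let d = Test 2 minus Test 3 in log10, the combined fluid and agar effect. It is not in the documents; I use -0.2 to +0.3. The between-replicate SD is not given either; I use 0.05 log10, with 0.10 as a check.

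**Algebra.** Let k be the log10 kill by residue, so Test 1 = Test 2 - k. Then

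Test 3 - Test 1 = (Test 2 - d) - (Test 2 - k) = k - d.

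The wording of (d) passes when k - d ≤ 0.20, that is k ≤ 0.20 + d. The share of organisms killed is 1 - 10^(-k). A rule on Test 2 - Test 1 passes when k ≤ 0.20, whatever d is.

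**Chance of passing.** I simulated Poisson plate counts, with Test 3 at 55 CFU/ml, replicate SD 0.05 and a true residual kill of 0.30 log10 (50%). The last two columns give the pass probability at one time point for one product and organism.

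| d | Largest k passing (d) | Killed | Passes (d) as worded | Passes Test 2 - Test 1 ≤ 0.20 |
|---|---|---|---|---|
| -0.2 | 0 | 0% | 0% | 5.7% |
| -0.1 | 0.10 | 21% | 0% | 4.5% |
| 0 | 0.20 | 37% | 3.7% | 3.5% |
| +0.1 | 0.30 | 50% | 49.2% | 3.1% |
| +0.2 | 0.40 | 60% | 96.9% | 2.5% |
| +0.3 | 0.50 | 68% | 100% | 2.2% |

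Requiring both conditions, at 50 CFU/ml and the same SD, gives 1 to 3% at d = 0, 0.1 and 0.2. At SD 0.10 and 55 CFU/ml the contrast at d = 0.2 is weaker but still large: 86.8% under (d) against 12.5% under the Test 2 rule.

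**The opposite direction.** With no residual kill and d = -0.2 (55 CFU/ml, SD 0.05), (d) passes only about 50% of the time and the Test 2 rule about 100%. There (d) errs toward failing adequate neutralization.

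**Cost of the added condition.** Three products, two organisms and two time points give 3 × 2 × 2 = 12 checks. With no residual kill, d = 0, 50 CFU/ml and SD 0.05, all 12 pass 99.9% of the time under (d) alone and 99.8% with the added condition. At 30 CFU/ml and SD 0.10 the figures are 84% and 72%.

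**The bracket in (d).** Item (f) requires Test 4 ≤ Test 3 - 0.20. Read literally, the bracket passes when Test 1 ≥ Test 4 - 0.20. Test 1 could then lie 0.20 + 0.20 = 0.40 log10 below Test 3, or lower still if Test 4 is lower. This is a separate and more definite error; correcting it to Test 3 does not supply the missing Test 2 comparison.

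**The case against.** The strongest reply is that nothing in the documents shows d to be positive. The hazard that Appendix 17.7.1 and item (e) address is toxicity, which means lower recovery in SSF++. In that case (d) is the harder test. All three tests are inoculated in the same manner, and comparing at corresponding time points means that decline in PBW over 30 minutes could not mask kill already present at the first plating. The validation also uses the groin application procedure on the smaller treatment area (17.7.7), which is demanding relative to the abdominal application. All of this stands. It makes the gap conditional but does not close it, because no rule checks the sign or the upper size of d.

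A reader might go further in four ways that the documents do not support.

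- Item (g) might be read as letting Test 3 fall across its whole range between platings. But it says "The amount of CFU added for each aspect must be confirmed to yield a final suspension containing 30-100 CFU/ml (validated in test 3", which is a check on the inoculum and not an acceptance range for survival.
- The tolerated kill of 0.50 log10 at d = 0.3 might be equated with the 0.5 log10 non-inferiority margin. The first is absolute kill within one product; the second is a difference between products. Kill common to both products would largely cancel.
- Product A might be said to leave more residue because its applicator holds 26 ml. Table 2 gives A the same treatment areas and application times as B and C and a longer drying time, and there are no residue data.
- A limit on Test 3 drift might seem a natural addition, but the documents offer no basis for a value.

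The procedure follows an ASTM standard that was not available here, so whether that standard prescribes the viability control as comparator is left open.

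**Conclusion.** The gap is real but conditional. As worded, (d) passes a residual kill of up to 0.20 + d log10, and (e) does not limit d from above. The excess over the intended 0.20 exists only if SSF++ on TSA+N recovers more than PBW on TSA. A reader might infer that inadequate neutralization will pass; the documents do not support that, because d is unknown and a negative d hides nothing. The tolerated-kill figures rest on the assumed range of d, and the pass probabilities also rest on the assumed replicate SD. This is a cheap improvement to the acceptance rules, not evidence that the neutralizer fails or that the efficacy comparisons are biased.

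**What to change.** Make one edit to Appendix 17.7.10:

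1. Keep (d) against Test 3, and correct its bracketed formula so that it subtracts Test 1 from Test 3 instead of from Test 4.
2. Add to (d) that mean log10 Test 2 minus mean log10 Test 1 must also be at most 0.20, at each corresponding time point, for each product and each organism.
3. Amend (c) so that Test 1 is compared with both Test 2 and Test 3.

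All the plates are already planned in 17.7.8.2, so the edit itself adds no subjects, samples or laboratory work. The downside is a slightly higher chance of having to repeat the validation, mainly if replicate variability is high. A repeat could need new subjects and another 7-day washout (17.7.3). Keeping (d) also keeps its strictness when d is negative.

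### Section 17.7.10 d) states the neutralizer limit against Test 3 but prints the calculation as Test 4 minus Test 1, which is laxer whenever item f) is met at the same time point

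*Combined protocol and SAP*

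**What the plan says.** Section 17.7.10 lists the rules for judging the neutralization control. Four of them matter here.

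- Item c) makes Test 3 the common comparator: Tests 1, 2 and 4 "will be compared to the test microorganism viability population (Test 3").
- Item d) is the effectiveness rule. It begins "Neutralization aspects of the SSF++ will be considered adequate if the mean" and, in words, allows Test 1 to lie at most 0.20 log10 below Test 3. The bracket that follows gives the calculation with a different first term, "CFU/ml from Test 4 – Mean" of Test 1, at matching time points.
- Item e) is the toxicity rule and is built the same way. Its words and its bracket agree: the bracket begins "CFU/ml from Test 3 – Mean" and subtracts Test 2.
- Item f) covers product activity: "CFU/ml from Test 4 must be at least 0.20" log10 below Test 3. It names no time point.

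The two candidate terms are different experiments. Test 3 (17.7.8.2.3) is the organism in phosphate-buffered water with no product. Test 4 (17.7.8.2.4) has no neutralizing step: "A 5.0 mL aliquot of the investigational product or active control will be inoculated with a volume of the challenge microorganism", and "Triplicate 0.75 mL aliquots will be removed and plated using TSA pour plates", that is, on agar without neutralizers. The inoculum "must be confirmed to yield a final suspension containing 30-100 CFU/ml (validated in test 3").

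**The concern.** The sentence and its bracket define different quantities, and item d) is the rule that decides whether the neutralizer works. Sections 5.2.3 and 17.7.2 give the purpose of the control: to show that the sampling fluid and media inactivate the products. Of the criteria in 17.7.10, only d) puts a limit on that. Item e) concerns toxicity, f) product activity, g) the inoculum and h) sterility, while c) sets no limit.

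A worksheet built from the bracket would judge recovery in neutralized samples against survival in the product itself. A poor neutralizer could then be accepted.

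This bears on the main study because section 5.2.2 lets samples stand for up to 30 minutes before plating, the interval covered by the second Test 1 count in 17.7.8.2.1. Product activity that continued in the tube would lower post-application counts but not baseline counts, which are taken before application. That is a direction only; the documents do not support a size.

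**Working it through.** **Notation.** T1, T3 and T4 are the mean log10 CFU/ml of Tests 1, 3 and 4 at one time point.

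**Inputs, all from 17.7.10.** Limit 0.20 log10 (item d); T3 − T4 ≥ 0.20 (item f); inoculum window 30 to 100 CFU/ml, validated in Test 3 (item g).

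**1. The rule in words.** T3 − T1 ≤ 0.20, so the lowest accepted T1 is T3 − 0.20. The largest accepted loss is 1 − 10^(−0.20) = 1 − 0.631 = 36.9%. In counts, the floor is:
- Test 3 at 30 CFU/ml: 30 × 0.631 = 18.9 CFU/ml
- Test 3 at 100 CFU/ml: 100 × 0.631 = 63.1 CFU/ml

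**2. The rule in the bracket.** The bracket has no limit of its own. Taking the sentence's limit as an assumption, T4 − T1 ≤ 0.20, so the lowest accepted T1 is T4 − 0.20. Adding T3 − T4 to both sides gives T3 − T1 ≤ 0.20 + (T3 − T4).

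**3. Difference between the rules.** The floors differ by (T3 − 0.20) − (T4 − 0.20) = T3 − T4.
- T4 below T3: the bracket is laxer.
- T4 equal to T3: the rules coincide.
- T4 above T3: the bracket is stricter.

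**4. With item f) met at the same time point.** T3 − T4 ≥ 0.20, so the accepted loss is at least 0.20 + 0.20 = 0.40 log10, or 1 − 10^(−0.40) = 1 − 0.398 = 60.2%. The time-point condition is needed because d) matches time points and f) names none.

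**5. Size for a range of gaps.** Only the first gap, item f)'s limit, comes from the documents; the others are assumed.

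| T3 − T4 (log10) | Accepted Test 1 loss under the bracket (log10) | Recovery relative to Test 3 | Floor, Test 3 = 30 CFU/ml | Floor, Test 3 = 100 CFU/ml |
|---|---|---|---|---|
| 0.20 | 0.40 | 39.8% | 11.9 | 39.8 |
| 0.50 | 0.70 | 20.0% | 6.0 | 20.0 |
| 1.00 | 1.20 | 6.3% | 1.9 | 6.3 |
| 1.40 | 1.60 | 2.5% | 0.8 | 2.5 |

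Under the words, the floors stay at 18.9 and 63.1 CFU/ml for every row.

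**6. Limiting case.** If T1 = T4, the bracket gives 0.00 and passes, although recovery after neutralization is then no better than survival in the product.

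**7. With the bracket corrected.** T3 − T1 ≤ 0.20 restores the worded limit (recovery of at least 63.1%), agrees with item c) and has the same form as item e).

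**The case against.** The best defence is that the operative rule is clear without the bracket. The limit stands in the sentence, the sentence names Test 3, and items c) and e) confirm it, so this looks like a one-digit slip rather than a rival criterion. The figures above belong to a hybrid rule that the plan never states: the sentence's limit applied to the bracket's difference. Nothing in section 9 uses the formula. All of this is correct, and it limits the weight of the point. It does not make the bracket right. The bracket is the only place where item d) spells out the calculation, and it contradicts the sentence it is meant to explain.

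A second argument is that Test 4 at item f)'s limit is an unrepresentative case. Counts could be very low or zero when 30 to 100 CFU/ml are placed in the product itself. The documents give no counts, so this remains an inference. With zero survivors, log10 is undefined, the bracket cannot be evaluated, and 17.7.10 gives no rule for that. This might make the slip easier to notice. However, a low Test 4 makes the bracket laxer still, and substituting a small value for zero would let almost any Test 1 result pass. The case at item f)'s limit is therefore the smallest effect under that condition, not an exaggerated one.

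Finally, this is an inconsistency between a sentence and its formula; no number in the plan has been miscalculated. That is fair as a description and leaves the correction unchanged.

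**Conclusion.** The concern holds. Item d) contradicts itself, and the bracket carries the wrong term. Used with the 0.20 limit, the bracket accepts a Test 1 loss of 0.20 + (T3 − T4) log10 instead of 0.20. That is at least 0.40 log10 (60% instead of 37%) when item f) is met at the same time point.

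This size rests on two assumptions: the laboratory calculates from the bracket, and it applies the sentence's limit to the result. If it follows the words, nothing changes. The documents do not allow any statement about an effect on A-C or B-C. The point should be fixed because it sits in the only criterion with a limit on neutralizer effectiveness.

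**What to change.** In 17.7.10 d), replace Test 4 by Test 3 as the first term of the bracket. It then gives the mean log10 of Test 3 minus that of Test 1, matched by time point as it is now.

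If the control has already been run, confirm which formula was used and recompute item d) from the recorded counts at both time points.

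The cost is one term in an appendix and, at most, a recalculation. No new subjects or samples are needed.

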#### 17.7.11 Controls

Absence of growth control:

Triplicate plates of TSA and TSA+N used will be incubated with the test. In addition, triplicate 1.0 ml aliquots of SSF++ and PBW will be plated using TSA. All plates will be incubated with the test.

### 17.8 Skin Irritation Rating Scale

Skin Irritation Scoring System		
Condition	Rating	Description
Erythema	0	No reaction
	1	Mild and/or transient redness limited to sensitive area
	2	Moderate redness persisting over much of the product-exposed area
	3*	Severe redness extending over most or all of the product-exposed area
Edema	0	No reaction
	1	Mild and/or transient swelling limited to sensitive area
	2	Moderate swelling persisting over much of the product-exposed area
	3*	Severe swelling extending over most or all of the product-exposed area
Rash	0	No reaction
	1	Mild and/or transient rash limited to sensitive area
	2	Moderate rash persisting over much of the product-exposed area
	3*	Severe rash extending over most or all of the product-exposed area
Dryness	0	No reaction
	1	Mild and/or transient dryness limited to sensitive area
	2	Moderate dryness persisting over much of the product-exposed area
	3*	Severe dryness extending over most or all of the product-exposed area

\* A score of 3 in one or more of the conditions evaluated represents significant irritation and qualifies as an Adverse Event.

